7.2.4. Treatment Visit 3 (Day 4 +/- 0 day)

The following observations/ procedures are to be performed and checked:

- FAAM-ADL (+/- 1 hour related to baseline assessment time whenever possible)
- Removal of the elastic bandage by the team member exclusively responsible for handling the study medication
- Ankle sprain-related measurements: VAS for evaluating pain at rest and pain on passive movement (+/- 1 hour related to baseline assessment time whenever possible)
- Review of rescue medication and IMP usage recorded in the patient diary and transfer data into the eCRF
- Check other pain medication and/or RICE use with the patient (both are prohibited), record on medical records and enter into the eCRF if any
- Record any change in other concomitant medications
- Record use of arm crutches
- Evaluation and recording of any AEs the patient has experienced since the last visit including a possible re-injury of the ankle and adverse events observed at the site of administration of the IMP. SAE evaluation and reporting if applicable
- Collection of patient diary used from Day 1 to Day 4 and dispense patient diary to be used from Day 4 to Day 14
- Confirmatory check of grading. Patients with severity Grade 3 will be withdrawn from the study. No further data will be collected from these patients. Further treatment and taken care will be at discretion of the investigator according to the local medical practice.
- Drug accountability for IMP by weighing of study drug tube by the team member exclusively responsible for handling the study medication
- Application of IMP (and elastic bandage, if still required) by the team member exclusively responsible for handling the study medication
- Drug accountability for rescue medication
- Dispense 500 mg paracetamol tablets (one box containing 20 tablets) as rescue medication for pain relief (if needed). Instruct the patient that he/she is further not allowed to take any analgesic medication other than the rescue medication (paracetamol) provided by the study site staff with a maximum dose of four tablets or 2000 mg/day, but not more than 2 tablets at a time. He/she will not be allowed to take any paracetamol tablets within 24 hours prior to visit 4.

-
- Instruct patients to return to next visit (+/- 1 hour related to baseline assessment time) and return patient diary, IMP and remaining rescue medication.

7.2.5. End of Treatment Visit (Visit 4; Day 7 +/- 1 day) or Discontinuation of Treatment Visit if applicable

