9.3.1.2 Additional Operationalizations

- Visit 4 (Day 7) will be introduced as additional primary endpoint in the chain of a priori ordered hypotheses, leading to the following final sequence of confirmatory analyses:
 - 1. AUC for pain on passive movement in VAS from baseline to Day 4 (test for superiority, Traumed® gel versus placebo)
 - 2. AUC for pain on passive movement in VAS from baseline to Day 4 (test for non-inferiority, Traumed® gel compared to diclofenac gel)
 - 3. AUC for pain on passive movement in VAS from baseline to Day 7 (test for superiority, Traumed® gel versus placebo)
 - 4. AUC for pain on passive movement in VAS from baseline to Day 7 (test for non-inferiority, Traumed® gel compared to diclofenac gel)

If the preceding *a priori* ordered test shows statistical significance, the subsequent hypothesis can then be tested individually in a confirmatory manner according to the principle of *a priori* ordered hypotheses (for control of alpha using stepwise testing see [Maurer et al. 1995]).

Comment: The original endpoints at Day 4 remain unchanged (hypotheses no. 1 and no. 2), however Day 7 is introduced as additional primary endpoint in the chain of *a priori* ordered hypotheses (hypotheses no. 3 and no. 4). This addition is implemented as per BDRM decision in order to avoid lack of assay sensitivity at the early stage of the ankle joint injury (C1502_MTG_NOTES_BDRM_09MAR2021_20210324).

- Descriptive procedures will be performed according to section 9.1.
- For the analysis of covariance, in addition to the table with descriptive statistics and the
 analysis of variance of the covariate (test for homogeneity of the groups with respect to
 the covariate), the following results of the analysis of covariance will be generated:
 - Analysis of covariance of the full model (separate regression lines for each group) with the following information:
 - Test for parallelism and group difference at X₀ as an indication of group differences in case the regression lines are not parallel (for the hypothesis of parallelism a 10%-level will be applied).

- Model parameter: for each group, the point of intersection of the regression line, the slope and the adjusted mean value of X₀, the common mean value of the covariates for all groups.
- Analysis of covariance for the reduced regression model (a single regression line for all groups for the assumption that the regression lines are parallel), with the following information:

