9.7 Analysis Populations

9.7.1.1 Operationalizations in Final Protocol

Safety Analysis Set: Randomized patients who receive at least one dose of investigational medication will form the Safety Analysis Set. The Safety Analysis Set will be used for all analyses of safety, tolerability, and background characteristics. For this set, the exposure to IMP will be also analysed.

Full Analysis Set (FAS): The Full Analysis Set is a subset of the Safety Analysis Set consisting of all patients with acute unilateral Grade 1 or Grade 2 sprain of the lateral ankle, for whom both baseline and Day 4 VAS values of pain are available. The Full Analysis Set will be used for the Intent-to-Treat (ITT) analysis.

Per-Protocol (PP) Set: Patients in the Full Analysis Set without major protocol deviations will form the PP Set. The PP Set will be used for the per-protocol analysis of the efficacy parameters. The same efficacy evaluations as in the FAS are planned. Relevant differences between the FAS and PPS will be evaluated in the Clinical Trial Report.

Protocol deviations will be collected during the entire trial and will be classified as minor or major at the Blind Data Review Meeting (BDRM). Protocol deviations that may affect the efficacy outcome of participants will be classified as major. The decision about major protocol deviations and assignments to populations will be documented in the BDRM minutes.

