9.7.1.2 Additional Operationalizations

- In order to preserve validity and integrity of the trial, all confirmatory and secondary analyses will be based on the group of non-issue patients (for details see section 8 Changes to the Protocol). As stated in the 'Amendment Summary Document for Substantial Protocol Changes', the sample size was proactively enhanced to ensure planned power and validity for evaluating the pre-defined trial objectives also in case that only non-compromised cases allow valid and unbiased conclusions. Results of issue patients will be provided separately in the Appendix of the Clinical Trial Report (CTR).
- FAS: VAS availability at Day 4 is referring to LOCF (primary analysis).
- PP: premature discontinuations due to "lack of efficacy", "adverse event", or
 "lack of efficacy" and "adverse event" (i.e. drug-related premature
 discontinuations) will not be excluded from the PP analysis, regardless of any
 existing protocol deviation. Benchmarks for "Major Protocol Deviation" (final
 BDRM decisions):
 - Grade 3 determination after Visit 3
 - VASPM V1 < 50
 - Missing VASPM at V1 or V3 (Related to ,Data as Available')
 - Visit 2 \leftrightarrow Day 2 (Protocol Day 2)
 - Visit 3 < Day 4 or > Day 5 (Protocol Day 4 + 1 Day)
 - Visit $4 < \text{Day } 6 \text{ or } > \text{Day } 9 \text{ (Protocol Day } 7 \pm 1 \text{ day)}$
 - Compliance < 80% at V3 or V4
 - Premature Discontinuation (not drug-related)
 - The analysis populations (Safety, FAS, and PP) are listed individually in the Appendix of the final Statistical Analysis Plan.

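### SAP 9.7.1.2 keeps Day 9 visits in the per-protocol set although the protocol window it cites for Visit 4 ends on Day 8, and it gives no reason

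*SAP*

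**What the plan says.** - **Protocol window.** The heading of protocol 7.2.5 reads "End of Treatment Visit (Visit 4; Day 7 +/- 1 day". Protocol Table 1 and the SAP's copy of the schedule (6.2) give the same window.
- **PP rule for Visit 4.** SAP 9.7.1.2 makes the visit a major deviation if it is before Day 6 or, in the text as read, "> \text{Day } 9 \text{ (Protocol Day } 7 \pm 1" day.
- **PP rule for Visit 3.** The line above it in the same list reads "Visit 3 < Day 4 or > Day 5 (Protocol Day 4 + 1 Day".
- **How PP is formed.** SAP 9.7.1.1: "Patients in the Full Analysis Set without major protocol deviations will form the PP Set". The blind data review meeting grades deviations as minor or major, and the criterion is: "Protocol deviations that may affect the efficacy outcome of participants will be classified as major".
- **Where PP is used.** Protocol 11.1.3 and the synopsis reproduced in SAP 6.1 make PP the primary set for non-inferiority. SAP 9.3.1.1 assigns hypothesis 2 (Day 4) to PP. SAP 9.3.1.2 adds, as hypothesis 4, "AUC for pain on passive movement in VAS from baseline to Day 7 (test for non-inferiority, Traumed® gel compared to diclofenac gel", without naming an analysis set.
- **Time basis.** All AUCs use the actual time of measurement (protocol 11.1.3, SAP 9.3.1.1). Neither document mentions dividing by elapsed time.

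**The concern.** The line quotes a window and then applies a different one. The lower limit equals the protocol's; the upper limit is a day later. The Visit 3 line reproduces the window it cites. SAP section 8, section 9.7 and appendix 13.1 do not explain the extra day, although section 8 and 13.1 do explain other decisions of the blind data review.

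The timing of Visit 4 matters more than it did under the protocol, because the SAP moves the Day 7 AUC from the secondary variables into the confirmatory sequence. Visit 4 supplies the last pain score of that AUC. Because elapsed time is not normalised, a later visit raises the AUC even when pain is the same, so visit timing plausibly meets the SAP's own criterion for a major deviation. What is at stake is who belongs to the set used for the non-inferiority tests, and whether that set follows the rule it claims to follow.

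**Working it through.** **1. The window**

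| Visit | Window cited in the SAP line | Days kept by the SAP rule | Match |
|---|---|---|---|
| Visit 3 | Day 4 + 1 day: Day 4 to 5 | Day 4 to 5 | yes |
| Visit 4, lower limit | 7 − 1 = Day 6 | Day 6 | yes |
| Visit 4, upper limit | 7 + 1 = Day 8 | Day 9 | no |

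The only day kept by the SAP but outside the cited window is Day 9. (The Visit 3 line follows Table 1; the heading of protocol 7.2.4 gives Day 4 +/- 0 day.)

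**2. Elapsed time from Day 1**

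- Nominal Day 7: 7 − 1 = 6 days.
- Protocol limit, Day 8: 8 − 1 = 7 days; 7/6 = 1.17.
- SAP limit, Day 9: 9 − 1 = 8 days; 8/6 = 1.33.

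The permitted range is 5 to 7 days under the protocol and 5 to 8 days under the SAP rule.

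**3. Effect on one patient's AUC (illustration)**

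Assumption: pain is flat over the extra time at 16.0 to 21.6 mm. This is the range of Day 7 medians in the earlier ankle sprain trial (protocol section 3). Extra AUC = extra days × pain level.

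- Day 9 against Day 7: 2 × 16.0 = 32.0; 2 × 21.6 = 43.2 mm x days.
- Day 9 against Day 8: 1 × 16.0 = 16.0; 1 × 21.6 = 21.6 mm x days.

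The only margin in the documents is 25 mm x days, derived in protocol 11.1.3 for the Day 4 AUC. SAP 9.3.1.2 gives none for Day 7, so 25 serves here only as a yardstick.

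**4. Effect on the difference between arms**

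If the share of Day 9 visits is equal in both arms, and pain over the extra time is similar, the extra AUC cancels. Otherwise, shift = difference in share × extra AUC against Day 7. The documents give no readable count of Day 9 visits, so the imbalances below are assumed.

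| Imbalance | At 16.0 mm | At 21.6 mm | Share of 25 |
|---|---|---|---|
| 2 points | 0.02 × 32.0 = 0.64 | 0.02 × 43.2 = 0.86 | 2.6% to 3.5% |
| 5 points | 0.05 × 32.0 = 1.60 | 0.05 × 43.2 = 2.16 | 6.4% to 8.6% |
| 10 points | 0.10 × 32.0 = 3.20 | 0.10 × 43.2 = 4.32 | 12.8% to 17.3% |

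Measured against a Day 8 visit, these shifts are half as large. An excess of Day 9 visits on diclofenac gel would favour non-inferiority, and an excess on Traumed gel would count against it.

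**5. Which tests are touched**

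A Day 9 pain score does not enter the Day 4 AUC. PP is a single set of patients, however, so the limit affects membership for hypothesis 2. For hypothesis 4 it affects both membership and the AUC value, if PP is the set used.

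**The case against.** The strongest answer is that the list sets thresholds for severity and does not copy the visit schedule. The blind data review may grade a Day 9 visit as minor, and PP excludes only major deviations. Other entries are also looser than the protocol: inclusion requires pain above 50 mm, while the benchmark is below 50, and Visit 5 has a window but no benchmark. The reason may be in the review meeting's minutes, which the SAP cites but which are not part of the documents. The individual assignments (SAP 13.2) were not readable either. The text was machine-read, and the Visit 2 line is visibly garbled. An original ≥ Day 9 would mean the same as > Day 8 and would remove the mismatch.

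Much of this stands. A deliberate tolerance is possible, and a reading error must be excluded first. But the looser entries do not cite a protocol figure beside a different one. This line does, and a deliberate extension should be visible in the plan.

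Two stronger readings do not hold:

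- **A reader might infer that the Day 7 non-inferiority result is biased.** The limit comes from a blind review, no count by arm is readable, and the shift needs an imbalance. Hypothesis 4 is also last in the sequence and is confirmatory only if the first three succeed. That PP decides it follows from the general rule and by analogy with hypothesis 2, since the added list names no set.
- **A reader might infer that Day 9 patients were treated beyond the stated course.** The documents do not say what happens to dosing between Day 7 and a late Visit 4. Treatment for 7 days (protocol 6.1.3) and a last application at Visit 4 (7.2.5) raise the same question at Day 8, inside the window. Those passages should be reconciled; they do not support a claim about Day 9.

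**Conclusion.** As the text reads, the SAP's PP limit for Visit 4 contradicts the window it cites by one day and gives no reason. The mismatch itself needs no assumption beyond a correct reading of the source page. It affects PP membership for the Day 4 non-inferiority test and, under the general rule on analysis sets, for the Day 7 test as well.

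The effect on a single Day 9 patient's AUC may be substantial, at 32 to 43 mm x days over a Day 7 visit under the flat-pain assumption. The effect on the comparison between arms is probably modest: about 0.6 to 4.3 mm x days for assumed imbalances of 2 to 10 percentage points, and near zero if the arms are balanced and pain over the extra time is similar. The documents establish neither a direction of bias nor the number of patients concerned. The line should be settled before unblinding because it defines a confirmatory analysis set and is cheap to settle.

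**What to change.** 1. Check the line on the SAP's source page. If it reads ≥ Day 9, nothing further is needed on this point.
2. If it reads > Day 9 and this was not intended, make Visit 4 a major deviation when it is before Day 6 or after Day 8, and recode the PP flags before unblinding.
3. If the blind data review meant to treat Day 9 as a minor deviation, say so in SAP 9.7.1.2 with the reason, and add a PP sensitivity analysis of the non-inferiority tests without Day 9 patients.
4. In either case, name the analysis set for hypotheses 3 and 4 in SAP 9.3.1.2, and report the number of Day 9 visits by arm after unblinding.

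The cost is one number and a recode, with perhaps a few patients lost from PP, or else one sentence and one extra analysis. SAP section 3 places sign-off before unblinding approval, so there is a natural point for the correction. A major change after sign-off has to be reported and justified in the clinical trial report under SAP section 11.

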10. SOFTWARE APPLIED

Unblinded clinical trial evaluation will be performed on high security PCs (HSPC) within a validated working environment at the department 'Clinical Research/Biometry' in the institute IDV Data Analysis and Study Planning under supervision of [name]., C. Stat. (RSS), with a 'Certificate Biometry in Medicine GMDS'.

Software packages to be used for unblinded analyses and generation of Clinical Trial Report (CTR):

- TESTIMATE V6.5.14 (statistical analyses)
- SCIENCEGRAPH V4.9.39 (scientific figures)
- ICH-Study-Report-Manager V2.4.3 (Clinical Trial Report)

11. POST HOC CHANGES TO PLANNED ANALYSES (POST UNBLINDING)

Any major changes to this plan after final sign-off will be specified in the Clinical Trial Report of the final analyses with corresponding scientific rationales.

13. APPENDIX

13.1 BDRM Decisions

13.1.1 Problem Cases

Besides the 'issue' cases addressed in C1502 Study Protocol Version 4.0 (3 February 2020) and in the Amendment Summary Document for Substantial protocol Changes (3 February 2020), no other problem cases were identified. For details see section 8 *Changes to the Protocol*.

13.1.2 Other Decisions

Day 7 was introduced as additional endpoint in the chain of *a priori* ordered hypotheses (hypotheses no. 3 and no. 4). This addition was implemented as per BDRM decision in order to avoid lack of assay sensitivity at the very early stage of the ankle joint injury (C1502_MTG_NOTES_BDRM_09MAR2021_20210324).

13.3 Table of Contents for Data Displays (Items of eCRF)

All items of the eCRF will be presented in individual participant data listings and in appropriate summary tables. Standard descriptive summary statistics will be calculated for continuous and semi-continuous variables (i.e., arithmetic mean, standard deviation, standard error of the mean, minimum value, lower quartile, median, upper quartile, maximum value, number of non-missing values). In addition, measures for skewness and kurtosis will be provided for suitable efficacy variables. Categorical data will be presented in frequency tables using counts and their associated percentages. Individual participant data listings will be presented per eCRF item and will be sorted appropriately. Summary tables will be displayed by treatment conditions and visit (if applicable). Where appropriate, the presentation will include changes from baseline. Semi-quantitative and quantitative efficacy data will be additionally visualized by boxplot diagrams. All standardized effect sizes (Mann-Whitney) will be visualized with their corresponding 95%-confidence intervals. All standard statistical tables will be generated applying the standard table layout of the validated statistical package TESTIMATE V6.5.14 (IDV Gauting). Associated meta-data and variable labels are finalized before unblinding All standard scientific figures are generated applying the standard figure layout of the validated scientific package SCIENCEGRAPH V4.9.39 (IDV Gauting).

KLIFO-013.05-A1.02

Data displays will be provided for the following analysis sets:

Chapter Title	Analysis set
Study Patients	A: All patients randomized
Demographic and Other Baseline Characteristics	B: Safety analysis set C: Full analysis set D: Per-protocol analysis set
Treatment Compliance	B: Safety analysis set C: Full analysis set D: Per-protocol analysis set
Visits	B: Safety analysis set C: Full analysis set D: Per-protocol analysis set
Analysis of Efficacy	C: Full analysis set D: Per-protocol analysis set
Analysis of Concomitant/ Supportive Therapies	B: Safety analysis set C: Full analysis set D: Per-protocol analysis set
Analysis of Safety	B: Safety analysis set

13.3.1 Tables

Study Patients

Sections
Disposition of Patients
End of Study / End of Treatment
Inclusion/Exclusion Criteria
Major Protocol Violations
Analysis Sets

Demographic and Other Baseline Characteristics

Chapter Title
Demography
Pregnancy Test
Medical History
Physical Examination / Vital Signs
Prior and Concomitant Medications
Time and Grading of Injury / Confirmatory Check of Grading
Supportive Therapy
VAS
FAAM

Treatments

Chapter Title
Study Drug Administration
Compliance

Visits

Chapter Title

Visits Intervals

Efficacy Analysis

Chapter Title

VAS Pain on Passive Movement at Visits

AUC for VAS Pain on Passive Movement at Visits

VAS Pain at Rest at Visits

AUC for VAS Pain at Rest at Visits

Time to 50% Improvement for VAS Pain at Rest at Visits

Rescue Medication

Concomitant/ Supportive Therapies

Chapter Title

Other Pain Medication

Supportive Therapy

Concomitant Medications

Safety Analysis

Chapter Title

Extent of Exposure

Adverse Events

Physical Examination / Vital Signs

13.3.2 Listings

Study Patients

Sections
Disposition of Patients
End of Study / End of Treatment
Inclusion/Exclusion Criteria
Major Protocol Violations
Analysis Sets

Demographic and Other Baseline Characteristics

Chapter Title
Demography
Pregnancy Test
Medical History
Physical Examination / Vital Signs
Prior and Concomitant Medications
Time and Grading of Injury / Confirmatory Check of Grading
Supportive Therapy
VAS
FAAM

Treatments

Chapter Title
Study Drug Administration
Compliance

Visits

Chapter Title

Visits Intervals

Efficacy Analysis

Chapter Title

VAS Pain on Passive Movement at Visits

AUC for VAS Pain on Passive Movement at Visits

VAS Pain at Rest at Visits

AUC for VAS Pain at Rest at Visits

Time to 50% Improvement for VAS Pain at Rest at Visits

Rescue Medication

Concomitant/ Supportive Therapies

Chapter Title

Other Pain Medication

Supportive Therapy

Concomitant Medications

Safety Analysis

Chapter Title

Extent of Exposure

Adverse Events

Physical Examination / Vital Signs

13.3.3 Figures

Efficacy analysis

Chapter Title	Type of Figure
VAS Pain on Passive Movement at Visits	Boxplots across all points in time (per group and visit); Means with standard deviation across all points in time (per group and visit); Standardized effect sizes (MW) with CI across all points in time (per group and visit)
AUC for VAS Pain on Passive Movement at Visits	Boxplots across all points in time (per group and follow-up visit); Means with standard deviation across all points in time (per group and follow-up visit); Standardized effect sizes (MW) with CI across all points in time (per group and follow-up visit); Scattergram for primary endpoint at Day 4 with regression lines (baseline VAS as covariate)
VAS Pain at Rest at Visits	Boxplots across all points in time (per group and visit); Means with standard deviation across all points in time (per group and visit); Standardized effect sizes (MW) with CI across all points in time (per group and visit)
AUC for VAS Pain at Rest at Visits	Boxplots across all points in time (per group and follow-up visit); Means with standard deviation across all points in time (per group and follow-up visit); Standardized effect sizes (MW) with CI across all points in time (per group and follow-up visit)

Time to 50% Improvement for VAS Pain at Rest at Visits	Kaplan Meier Curves per group.
Rescue Medication	Boxplots for Day 1 to 4 Totals per group, Boxplots for Day 1 to Final Day Totals per group; Standardized effect sizes (MW) for Day 1 to 4 Totals and Day 1 to Final Day Totals with CI per group.

13.4 Clinical Trial Report (CTR) Specifications

13.4.1 Core CTR Specifications

The Core Clinical Trial Report (CTR) will be generated by means of the idv ICH-Study-Report-Manager V2.4.3 within the validated working environment at the department 'Clinical Research/ Biometry' in the institute IDV Data Analysis and Study Planning. The generation is based on the idv CTR template according to idv SOP KLIFO-16.04, the template being finalized before breaking the blind. The following specifications will apply to the CTR:

- Layout is DIN A4 format
- Body text font is Times New Roman 12 pt
- Language is American English (AE)
- CTR Structure is following the idv template according to idv SOP KLIFO-16.04
- CTR protocol sections are cited in original wording (unchanged or in past tense), the same applies to CTR SAP sections
- Scientific tables will be imported with full audit trail via validated pathway of module *idv-Tabellen/-Text*, remaining unchanged after import (original table)
- Scientific figures will be imported with full audit trail via validated pathway of module *idv Science-Graph-Tools*, remaining unchanged after import (original figure)
- Separate tables of content for core text, tables, and figures; generation by ICH-Study-Report-Manager V2.4.3
- CTR Versions:
 - Draft 0.1 (IDV Mock Report, generated before unblinding)
 - o Draft 1.0 (initial IDV CTR version after unblinding)
 - o Draft 1.X (follow-up CTR version after external review)
 - Draft to Final (IDV)
 - o Final (IDV)

13.4.2 Appendices:

- o Title pages generated according to title page of Core Report
- Appendix 1: Individual Patient Listing ('Non-Issue' Cases)
 - Listing of analysis data (validated XLI-export from TESTIMATE V6.5.14 analysis database with variable description by means of TESTIMATE V6.5.14 metadata)
- Appendix 2: Tables and Figures ('Non-Issue' Cases)
 - Tables will be imported with full audit trail via validated pathway of module idv-Tabellen/-Text, remaining unchanged after import (original scientific table)
 - Figures will be imported with full audit trail via validated pathway of module idv Science-Graph-Tools, remaining unchanged after import (original scientific figure)
- o Appendix 3: 'Issue" Cases
 - A. Individual Patient Listing (for specs see Appendix 1)
 - B. Tables and Figures (for specs see Appendix 2)
- Appendix 4: Listing of Original Raw Data Files (sas7bdat eCRF Domains) with variable description by means of latest version 4.0 of HE13226_eCRF Specification (02 June 2020), sorting as shown in Table 3.

Table 3: Sorting of Individual Patient Data (sas 7bdat raw data)

DOMAIN	DOMAIN TITLE	SORT BY
ADMIN	Study Drug Administration	SEQNO
AE	Adverse Events	SEQID
AEGO	Adverse Events flags	
CCG	Confirmatory check of Grading	VISITNO
COMMENTS DA	Rescue Medication	VISITNO
DIARYHO	Accountability Diary Handout	VISITNO
DM	Demography	
DOV	Visits	VISITNO
DS	Informed Consent	
EC	Exclusion Criteria	EXC
EOS	End of Study	
EOT	End of Treatment	
EVALP	Question to Patients	VISITNO
FAAM	about their treatment Foot and Ankle Ability Measure (FAAM) / Activities of Daily Living	VISITNO
GDD	(ADL) Subscale Date of Confirmation of Grade 3 - Discontinuation of Treatment	
GRAD	Time and Grading of Injury	VISITNO
IC	Inclusion Criteria	INC
LINK	Link list	
МН	Medical History	SEQNO
MHGO	Medical History flags	VISITNO
NA	Not Applicable	SEQNO
OPM	Other Pain Medications	STUDDCD
PARAC	Rescue Medication	STUDDCD
PCM	Prior and Concomitant Medications	CMSEQ

DOMAIN	DOMAIN TITLE	SORT BY
PCMGO	Prior and Concomitant Medications flags	
PE	Physical Examination	SEQNO
PEGO	Physical Examination flags	VISITNO
PREG RAND	Pregnancy Test (only for female patients with childbearing potential) Randomization	VISITNO
SUPT	Supportive Therapy	VISITNO
TAEC	Occurence of Adverse Events	VISITNO
TCMC	Occurence of Concomitant Medications	VISITNO
UNBLIND	Medical Code Broken	
VAS	Visual Analogue Scale	VISITNO
VS	Vital Signs	VISITNO
